# 1 Introduction

## 1.1 Objective of the Statistical Analysis Plan

The objective of this statistical analysis plan (SAP) is to provide a description of the general analytic strategy and the statistical methods that will be used to analyze the data for the TICO (Therapeutics for Inpatients with COVID-19) Phase III randomized, blinded, controlled, platform trial. This SAP applies to versions 3-5.1 of the TICO protocol. In version 2, two investigational agents are being studied, a SARS-CoV-2 neutralizing monoclonal antibody (nMAb) (Vir-7831) which is being developed by Vir Biotechnology (Vir) (San Francisco, CA) and GlaxoSmithKline (GSK) (Brentford, U.K.), and two nMAbs given sequentially (BRII-196 and BRII-198) which are being developed by Brii Biosciences (Durham, NC and Beijing). In protocol version 3, a third investigational agent is added, AZD7442, which is a combination of two nMAbs by AstraZeneca (Cambridge, U.K.); in version 4.0, MP0420, a DARPin® molecules was added; in version 5.0 (5.1), PF07304814, an antiviral protease inhibitor was added.

Participants are followed for death or re-hospitalization up to month 12 in version 2, and up to month 18 in versions 3, 4, and 5. The nMAbs and MP0420 are given by single infusion, or two sequential infusions for BRII-196 and BRII-198. PF07304814 requires a continuous infusion for 5 days.

The primary objective of the platform trial is to determine whether investigational agents, that are aimed at enhancing the host immune response to SARS-CoV-2 infection, or directly enhancing viral control in order to limit disease progression, are safe and superior to control (e.g., placebo) when given with standard of care (SOC) for the primary endpoint of time to sustained recovery evaluated up to 90 days of follow-up.

In the platform trial, several agents may be investigated in parallel, or staggered with overlapping times; investigational agents may be added or dropped. When more than one agent is being tested concurrently, where possible, participants will be randomly allocated across agents (as well as between the agent and its matched placebo), and the control group is pooled across the concurrently randomized, agent-specific matched placebo groups. Thus, each investigational agent and the corresponding pooled control group form their own randomized trial, and several agents may (at least partially) share their pooled control groups.

This SAP:

- Provides a short description of the study design (sections 1.2-1.4)
- Describes goals of the interim reviews by the independent DSMB and the planned format of the review meetings (section 2)
- Describes the planned data analyses presented in the reports to the DSMB (sections 3-13). General analysis principles are summarized in section 3, safety analyses are described in section 7, efficacy analyses in section 8, and interim monitoring guidelines in section 10.
- Describes data summaries to be provided regularly to study leadership to aid in monitoring trial conduct and data quality; these data summaries will be pooled across treatment groups, and will be restricted to enrolment, baseline data, and summaries of data completeness and study conduct.

The SAP for TICO will be updated by blinded study statisticians and clinical investigators following protocol amendments and prior to the unblinding the results for each investigational agent. For the latter, the blinded statisticians and clinical investigators will review data (pooled across treatment groups) on baseline characteristics, the number of participants who received a complete or partial infusion, and missing data due to withdrawal or loss to follow-up. A small group of the team will be unblinded to the pooled primary event rate to re-estimate sample size.

## 1.2 Description of the Study Design

This section is adapted from Section 1 of the TICO protocol versions 2.0 and 3.0.

### Design

TICO is a master protocol to evaluate the safety and efficacy of multiple investigational agents aimed at modifying the host immune response to severe acute respiratory syndrome coronavirus 2 (SARS-CoV-2) infection, or directly enhancing viral control in order to limit disease progression.

Trials within this protocol will be adaptive, randomized, blinded and initially placebo-controlled. Participants will receive standard of care (SOC) treatment as part of this protocol. If an investigational agent shows superiority over placebo, SOC for the study of future investigational agents may be modified accordingly.

The protocol is for a phase III randomized, blinded, controlled platform trial that allows investigational agents to be added and dropped during the course of the study for efficient testing of new agents against control (i.e., placebo + SOC) within the same trial infrastructure. When more than one agent is being tested concurrently, participants will be randomly allocated across agents (as well as between the agent and its placebo). For analysis, placebo groups of concurrently randomized agents will be pooled; therefore, control groups may overlap for different agents.

Randomization will be stratified by study site pharmacy and disease severity. There are 2 disease severity strata, defined as below:

- **Disease severity stratum 1:** Absence of all of the following: stroke, meningitis, encephalitis, myelitis, myocardial infarction, myocarditis, pericarditis, symptomatic congestive heart failure (NYHA class III or IV), arterial or deep venous thrombosis or pulmonary embolism, requirement for invasive mechanical ventilation, ECMO, mechanical circulatory support, vasopressor therapy, or new renal replacement therapy.
- **Disease severity stratum 2:** Presence of at least one of the excluded conditions or treatments in disease severity stratum 1.

The **primary endpoint** is the time from randomization to sustained recovery, defined as being discharged from the index hospitalization, followed by being alive and home for 14 consecutive days prior to Day 90. The definition of home will be operationalized as the level of residence or facility where the participant was residing prior to hospital admission leading to enrollment in this protocol.

An independent Data and Safety Monitoring Board (DSMB) will regularly review interim analyses that summarize safety and efficacy outcomes. For any agent, at the outset of the

trial, only participants in disease severity stratum 1 will be enrolled. This more restricted enrollment will continue until approximately 150 participants per study arm are enrolled and followed for 5 days. At this point, the DSMB will carry out a pre-specified assessment of futility, based on two 7-category ordinal outcomes (pulmonary and pulmonary+), assessed at Day 5. The pulmonary and pulmonary+ outcomes are described in [Appendix A](#). Safety of the investigational agents will also be assessed.

For investigational agents passing this initial futility assessment, enrolment of patients in disease severity stratum 1 will continue, and it is planned to also expand enrollment, seamlessly and without any data unblinding, to include participants in disease severity stratum 2. The expansion to include more severely ill participants will be subject to recommendations by the FDA and the DSMB based on safety considerations.

After the initial futility assessment is passed, future interim analyses will be based on the primary endpoint of sustained recovery and will use pre-specified guidelines to determine early evidence of benefit, harm or futility for the investigational agent.

### **Primary Objective**

The primary objective of this protocol is to determine whether investigational agents, aimed at enhancing the host immune response to SARS-CoV-2 infection, or directly enhancing viral control in order to limit disease progression, are safe and superior to control (e.g., placebo) when given with SOC for the primary endpoint of time to sustained recovery evaluated up to 90 days after randomization.

For all agents studied in TICO, the investigational agents/placebo have been given with study-supplied remdesivir unless contraindicated.

### **Duration**

Participants will be followed for 18 months following randomization in versions 3-5 of the protocol. Primary and most secondary outcomes will be collected during the first 90 days of follow-up only. Follow-up beyond 90 days is planned because the half-lives of some agents indicate that potentially meaningful amounts may remain in the body after 90 days of follow-up. After 90 days through the end of follow-up, hospitalizations and deaths will be ascertained.

### **Sample size**

This phase III trial is planned to provide 90% power to detect a 25% increase in the rate of sustained recovery for an investigational agent compared to placebo at the 0.025, 1-sided level of significance. This requires 843 primary events (i.e., participants who achieve sustained recovery). Randomization of 1,000 participants, equally allocated to each investigational agent and placebo, followed for 90 days is estimated to result in the required number of primary events. The event target may be achieved earlier if more than 1,000 participants are enrolled. Sample size will be evaluated periodically by study team members who are blinded to interim results on treatment difference and may be increased to maintain power for the hypothesized difference in sustained recovery between the investigational agent and placebo.

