## 1.4 Sample Size Estimates

The planned sample size for each pairwise comparison is 1,000 participants (500 participants in each group). The sample size is sufficient to detect a recovery rate ratio (RRR) of 1.25 for time to sustained recovery with 90% power, using a one-sided test with a significance level of 0.025. The treatment groups are compared using Gray’s test with  $\rho=0$ , the competing risks analogue of the log-rank test.

Sample size calculations are described in detail in Section 6.3 of the protocol.

Blinded sample size re-estimation will be carried out before enrollment is complete to determine whether the planned sample size of 1,000 participants followed for 90 days will yield the planned number of 843 primary events. The blinded sample size re-estimation does not involve unblinding of the treatment difference. It will be based on the pooled outcome data. Sample size may be increased to achieve the event target in the planned follow-up of 90 days. A

sample size increase may also be considered in order to achieve the event target before all participants are followed for 90 days.

When 300 participants (150 per study arm) are enrolled and have Day 5 outcome data, an early futility assessment is planned. This assessment will be based on two ordinal outcomes, denoted as “pulmonary” and the “pulmonary+”; both are ordered categorical outcomes with 7 categories, assessed on Day 5 (the two outcomes are described in [Appendix A](#)). Treatment groups will be compared using proportional odds models. With 300 participants, the early futility assessment is powered to detect a summary OR=1.60 with power of 95%, using a one-sided test with significance level of 0.30. Given the two-outcome decision rules, an investigational agent with a summary OR=1.60 at Day 5 for both outcomes, would pass the futility assessment with a power between 93% and 98%, and a type I error between 0.21 and 0.39.

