## 10.2 Early Assessment of Futility

### 10.2.1 Interim Monitoring Guidelines for Early Assessment of Futility

Early in the trial, enrolment is restricted to participants in disease severity stratum 1. When Day 5 data for the first (approximately) 300 participants (150 per study arm) are available, the DSMB will review interim data and use pre-specified guidelines for early evidence of sufficient activity of the investigational agent that justifies continuing enrolment for the agent and expanding eligibility criteria to include participants in disease severity stratum 2 as well as stratum 1. Because the risk-benefit trade-off may be more complex than can be captured in pre-specified guidelines, decisions to terminate an agent for futility will include a broad assessment of the available data, and may be postponed until more data is available.

The early futility monitoring uses two co-primary outcomes, denoted by “pulmonary” and “pulmonary+”, assessed on Day 5. Both are ordered categorical outcomes with 7 categories, described in section 4.1 of the protocol and in [Appendix A](#) to this SAP. The pulmonary outcome considers largely respiratory-related disease, similar to the ordinal outcome in the ACTT-1 trial. The pulmonary+ outcome has the same categories for pulmonary complications (e.g., requirements for oxygen), and additionally includes extra-pulmonary outcomes such as thrombotic, myocardial, and cerebral complications of COVID-19.

Guidelines for the early futility assessment are as follows:

- a. If the investigational agent is superior to placebo (i.e.,  $p \leq 0.3$  for a one-sided test) in both the pulmonary+ and pulmonary intermediate ordinal outcomes, then enrolment for the agent will expand to complete the trial.
- b. If there is insufficient evidence for superiority versus control (i.e., one-sided  $p > 0.3$ ) in each of the two outcomes, then stop randomization.
- c. If there is evidence (1-sided  $p < 0.3$ ) for an association for one endpoint and not the other, then the agent may or may not advance depending on the risk/benefit profile emerging from the data at this early stage. If the effect estimate for both outcomes is on the side of benefit, the preference would be towards advancing the agent and expanding enrollment to include disease severity stratum 2.

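### The 90% power is that of the final test alone; if the Day 5 futility guideline is followed as written, overall power is about 84-89% for RRR 1.25 with Day 5 OR 1.60

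*SAP*

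**What the plan says.** SAP section 1.2 (Sample size) attaches the power to the trial: "This phase III trial is planned to provide 90% power to detect a 25% increase in the rate of sustained recovery", "at the 0.025, 1-sided level of significance". It continues: "This requires 843 primary events", to be obtained from "Randomization of 1,000 participants, equally allocated to each investigational agent and placebo, followed for 90 days". Section 1.4 repeats the 90% for a comparison by Gray's test with rho = 0, described as "the competing risks analogue of the log-rank test". Section 8.1 (Assessment of model assumptions) repeats the 90% and the 843 events.

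Section 1.4 also describes the Day 5 assessment at 300 participants. For each ordinal outcome it "is powered to detect a summary OR=1.60 with power of 95%, using a one-sided test with significance level of 0.30". Under the two-outcome decision rules, an agent with OR 1.60 on both outcomes "would pass the futility assessment with a power between 93% and 98%, and a type I error between 0.21 and 0.39".

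Section 10.2.1 gives the rules:
- (a) One-sided p of 0.3 or less on both outcomes: enrolment expands.
- (b) One-sided p above 0.3 "in each of the two outcomes, then stop randomization".
- (c) Discordant results: the DSMB decides, with a preference for advancing when both estimates lie on the side of benefit.

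The same section calls these guidelines and lets the DSMB weigh all available data or postpone a futility decision.

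**The concern.** An agent with the design effect succeeds only if it first passes Day 5 and then wins the final test. The SAP gives a probability for each step but attaches the second one, 90%, to the whole trial. If 843 is exactly what one fixed test needs, nothing has been set aside for effective agents lost at Day 5, and the true chance of success is lower than stated.

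The loss arises on an intermediate outcome. Section 13.1 says it is still to be investigated whether that outcome adequately predicts sustained recovery. The SAP gives no link between RRR 1.25 and Day 5 OR 1.60, so the 93-98% pass probability depends on an effect size that need not accompany the design RRR. The DSMB and readers cannot see from the SAP how often an effective agent would be discarded.

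**Working it through.** **Inputs.** RRR 1.25, one-sided 0.025, 843 events, 1:1 allocation (section 1.2). Day 5: N = 300, OR 1.60, 95% power per outcome at one-sided 0.30; two-outcome pass probability 93-98% and type I error 0.21-0.39 (section 1.4). Assumption: correlation 0 to 0.5 between the Day 5 and final statistics. The documents give none; √(300/1000) = 0.55 would be the ceiling if the outcomes were perfectly correlated.

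**1. Reproduce the stated power.** Log-rank approximation: events = 4(1.960 + 1.282)² / (ln 1.25)² ≈ 844, rounded up to 845, against 843 stated. Power with 843 events: Φ(½√843 × ln 1.25 − 1.960) = Φ(3.239 − 1.960) = 0.8996. The 90% is therefore the power of one fixed test with no earlier stopping.

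**2. Reproduce the Day 5 figures.** From 95% power at one-sided 0.30, the standard error of the log OR is ln 1.60 / (0.524 + 1.645) = 0.217. Treat the two outcome statistics as bivariate normal with correlation 0.8:
- OR 1.60: both pass 92.5%; at least one passes 2 × 0.950 − 0.925 = 97.5%.
- OR 1.00: both 0.211; at least one 0.389.

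These match the stated 93-98% and 0.21-0.39. So 93% corresponds to stopping every discordant agent and 98% to advancing every one.

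**3. Apply the preference in rule (c).** If an agent advances when at least one outcome has p ≤ 0.30 and both estimates favour benefit, the pass probability at OR 1.60 is 96.7%.

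**4. Combine.** Overall power = P(pass Day 5 and final test significant). Under independence it is the product with 0.8996; otherwise it is a bivariate normal probability.

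| Handling of discordant results | Pass | Correlation 0 | 0.3 | 0.5 |
|---|---|---|---|---|
| All stop | 93% | 83.7% | 84.6% | 85.5% |
| Rule (c) preference | 96.7% | 87.0% | – | 88.0% |
| All advance | 98% | 88.2% | 88.5% | 88.9% |

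With no assumption on correlation, the lower limits are 0.8996 + 0.93 − 1 = 83.0% and 0.8996 + 0.98 − 1 = 88.0%. The upper limit is 90.0% in both cases.

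**5. Smaller Day 5 effects, same two-outcome rule and standard error.** The overall range runs from all discordant agents stopping at correlation 0 to all advancing at correlation 0.5.

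| Day 5 OR | Both pass | At least one passes | Overall power |
|---|---|---|---|
| 1.40 | 78.9% | 90.7% | 71-84% |
| 1.25 | 60.4% | 78.3% | 54-74% |

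Under the rule (c) preference the corresponding values are about 79-82% and 67-70%.

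**6. Later futility looks.** Simulating the 15% conditional-power threshold at 50% and 75% of events lowers final-test power from 89.98% to 89.83%. The material loss is at Day 5.

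**The case against.** The strongest reply is that nothing is miscalculated: every stated figure reproduces, and section 1.4 ties the 90% to a named test and gives the Day 5 pass probability alongside it. That is correct. The point concerns what the 90% is said to describe, since section 1.2 attaches it to the trial.

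Second, the Day 5 rules are non-binding. Only failure on both outcomes calls for stopping, about 2% of cases at OR 1.60, and the DSMB may postpone or weigh other data. This stands. The true figure lies between the as-written value and 90%, and 84% is an extreme, because rule (c) leans towards advancing. But the SAP itself quotes operating characteristics for the rule, so combining them for the rule as written is fair.

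Third, section 1.4 refers to protocol section 6.3 for details. The protocol document available is Appendix H1 only, so an overall power statement, or a link between RRR and Day 5 OR, may exist there. The absence can be claimed for the SAP only.

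Blinded sample size re-estimation does not answer the point: it protects the event target of the final test, not the chance of reaching that test.

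Three stronger readings are tempting but unsupported:
- A reader might infer that 843 events or 1,000 participants is wrong. Both figures suit the final test.
- A reader might quote the loss for smaller Day 5 effects from the pass rate of one outcome. The SAP's rule uses two, and the handling of discordant results widens the range considerably.
- A reader might carry the antibody-subgroup results of section 9.2 over to a diluted Day 5 OR. For time to recovery that section reports RRRs, and it gives no Day 5 ORs.

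**Conclusion.** The point holds as one of labelling. The 90% is conditional on reaching the final test. For an agent with RRR 1.25 and Day 5 OR 1.60 on both outcomes, overall power under the guideline as written is about 84% to 89%, and about 87-88% under the rule (c) preference. The likely shortfall is thus 2 to 3 points; about 6 points requires stopping every discordant agent with independent statistics.

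The result rests on the assumed correlation of 0 to 0.5, on adherence to the guideline, and on OR 1.60 accompanying RRR 1.25. If the Day 5 effect is smaller, the loss grows quickly. DSMB overrides reduce the loss, but power cannot exceed that of the final test. The figures do not apply to AZD7442, whose target is 1,228 events (Appendix E-2) and which has already passed Day 5 (section 10.2.2); they are relevant to agents still facing the assessment under the 843-event design.

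**What to change.** In sections 1.2, 1.4 and 8.1, state that 90% is the power of the final Gray's test with 843 events, conditional on passing the Day 5 assessment. Add that overall power is about 84-89% if RRR 1.25 is accompanied by Day 5 OR 1.60 on both outcomes, give the correlation assumed, and note that the guideline is non-binding.

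Add one sensitivity line computed under the two-outcome rule, with outcome correlation about 0.8: about 71-84% at Day 5 OR 1.40 and 54-74% at OR 1.25, the range running from stopping to advancing all discordant agents. If protocol section 6.3 already gives an overall figure, cite it and reconcile the two.

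The cost is a few lines of SAP text and a slightly less favourable headline figure. Sample size, event target, tests and monitoring boundaries stay as they are.

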### **Population**

The study population consists of inpatient adults ( $\geq 18$  years) who have had COVID-19 symptoms  $\leq 12$  days. Initially, enrollment is restricted to disease severity stratum 1. After a pre-specified review by the DSMB for safety and futility, when approximately 150 participants

are enrolled per study arm, eligibility for randomization will be expanded to also include patients in disease severity stratum 2, subject to recommendations by the FDA and DSMB.

### **Stratification**

Randomization is stratified by study site pharmacy; once enrolment is expanded to also include disease severity stratum 2, randomization will also be stratified by disease severity stratum.

### **Monitoring**

An independent DSMB will review interim data on a regular basis for safety and efficacy. An initial futility assessment will be performed after the first 300 participants (150 in the active and 150 in the placebo arms) are enrolled and have Day 5 data; this initial assessment is based on two ordinal outcomes (pulmonary and pulmonary+ outcomes at Day 5). Afterwards, the DSMB will use pre-specified guidelines to identify agents with clear evidence of efficacy for the primary outcome and, if so, recommend unblinding of the trial results for that agent. Conversely, the DSMB may recommend discontinuation of an investigational agent if the risks are judged to outweigh the benefits or if futility assessments indicate that there is low probability that an investigational agent will achieve statistical significance for the primary endpoint of sustained recovery.

For an investigational agent, if the trial is stopped early or if the trial continues until the pre-specified number of primary endpoints is reached, further enrollment of the investigational agent will be terminated if applicable, and the trial data for the investigational agent will be unblinded and reported with data through 90 days of follow-up. Follow-up of all participants will continue through 18 months (12 months in version 2.0 of the protocol) using the data collection plan described in the master protocol.

